Overall Study design	
The study aims to evaluate the lung cancer detection rate. Patients that previously were enrolled in SOS study will be called by project assistants and booked for DTS examination. In case the subject refuses to perform examination a phone interview for follow-up will be carried out acquiring information on the status of the subject, on the variation of quality of life, on smoke habits and on attitude toward lung cancer screening.
 
For the subject accepting the DTS examination the same questionnaire will be filled onsite just before examination. DTS will be then performed and blindly evaluated by two radiologists. DTS findings will be classified based on their dimension (large axis measurement), radiological characteristics (calcific, pleural, solid, partially solid and ground glass opacity) and position (in the 5 lobes). Findings will be then classified using LUNG-RADS [1]. The results of the DTS,in case of negative report, will be communicated with a letter to the patient.
 
The subjects with one or more nodules larger than 5 mm, not clearly benign, will undergo diagnostic contrast enhanced CT and will be followed according to Fleischner society [2] criteria.

	Discordant and positive cases will be discussed in a consensus session among radiologists and thoracic surgeons. The consensus results will be used in the following analysis.
Endpoints	
Primary
 
Lung cancer detection rate.
 
Secondary
 
 • Percentage of lung cancer addressed to radical surgery treatment; • Sensitivity of DTS evaluating the number of lung cancer occurred in the population of SOS study in the last 5 years; • Mortality • Overall survival (OS) • Quality of Life (QoL) • Cost-effectiveness
Eligibility criteria	
Inclusion criteria:
 
 • current or former smoker status; • for former smokers, the maximum time since quitting smoking must be below 10 years. • smoking history of at least 20 pack-years; • age 45-80 years; • no previous history of cancer in the 10 years before the beginning of the study; • be able to stand and hold the breath for 11 seconds during image acquisition • previous participation to SOS trial 
Exclusion criteria:
 
 • pregnancy

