Lung cancer is the leading cause of cancer-related death around the world, it represents 13% of all new cancer diagnoses [4]. The lung cancer incidence is gradually increasing, especially among women and young people, but the fraction of cured patient remains low. In 80% of cases lung cancer, in early phase, is treatable only with surgery without chemotherapy or adjuvant radiotherapy and the survival perspective at five years exceeds 70% [4]. Recently several studies [5,16] showed a relative reduction in lung cancer mortality of 20% in high-risk subjects enrolled in screening trials performed with low-dose Chest CT [7]. As a consequence, several of scientific guidelines recommended chest Computed Tomography (CT) in lung cancer screening. CT examination allows detection of small nodules and a good quality of the image but its disadvantages includes high cost and high radiation dose [8]. Digital tomosynthesis (DTS) is a limited angle tomography that allows reconstruction of coronal images from a set of projection acquired over a small angle of X-ray tube movement [9]. This technique is available in the AO Santa Croce e Carle since 2010 and more than 5000 have been executed with it. Several studies demonstrates that DTS is a reasonable alternative to the CT and allows a better evaluation of suspects nodules compared to conventional chest RX [11-13].

2. Objectives of the trial

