3.2. Exclusion criteria

[figure not shown]
Exclusion criteria:

- pregnancy

4. Trial Design

During this study, about 1700 subjects, who have been enrolled in SOS Observational Study will undergo a DTS. The study will be presented as an observational clinical trial and registered on clinicaltrials.gov. Initially, all the subjects that participated in the SOS study, will be contacted by phone and invited to perform a DTS in Carle Hospital. When accessing the hospital the subjects will be asked to fill-in a form to confirm that the inclusion criteria of the SOS study are still met. DTS will be then performed and blindly evaluated by two radiologists. DTS findings will be classified based on their dimension (large axis measurement), radiological characteristics (calcific, pleural, solid, partially solid and ground glass opacity) and position (in the 5 lobes). Findings will be then classified using LUNG-RADS[1] schema and ROC analysis will be applied. Inter-observer variability will be analyzed with Krippendorff's Alpha[17].

Discordant and positive cases will be discussed in a consensus session among radiologists and thoracic surgeons. The consensus results will be used in the following analysis. The subjects with one or more nodules larger than 5 mm, not clearly benign, will undergo diagnostic contrast enhanced CT and will be followed in line with Fleischner Society[2].

5. Evaluation criteria

Lung cancer will be histologically proven, following the procedure of Pathology Division that use a double blinded analysis of biological material.

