9.2. QoL instrument

In order to understand the impact of long-term psychosocial outcomes of lung cancer screening a QoL questionnaire will be adopted to measures the effectiveness of a screening program of the smoking habits of the subjects, anxiety and decision satisfaction. The reliability and validity of the questionnaire are highly consistent across different language-cultural groups.

10. Cost-effectiveness analysis

During the study the costs associated with the DTS procedure are evaluated, comparing them to those incurred for the execution of the CT in the subjects positive to the DTS.

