10.1. Methods

10.1.1. Type of Economic Evaluation.

Since a predictable variance in effectiveness, a cost-effectiveness analysis is justified.

10.1.2. Choice of Comparator.

The results are compared to the data obtained from the NELSON study and the National Screen Screening Trial for the evaluation of the effectiveness of screening in the control of 10-year mortality due to lung cancer.

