19.1. The study coordinator

The Study Chairman(in cooperation with the Data Center) will be responsible for writing the protocol, revising all case report forms and documenting his/her review on evaluation forms, discussing the contents of the reports with the Data Manager and the Statistician, and for publishing the study results. He will also, as a rule, be responsible for replying all clinical queries about eligibility, treatment, and the assessment of the patients.

20. Trial sponsorship and financing.

Santa Croce e Carle Hospital, thanks to a donation of Fondazione CRC, will cover costs of DTS examination, data organization, supervision and project assistance.

21. Trial insurance

Covered by Santa Croce e Carle Hospital

22. Appendix

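### Section 10 takes its CT cost from contrast-enhanced work-up CTs, but the comparator in 10.1.2 is low-dose CT screening, so cost and effect belong to different uses of CT

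*Combined protocol and SAP*

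**What the plan says.** Cost-effectiveness is a listed secondary endpoint (synopsis, Endpoints; also Section 2.2). Section 10 names one cost comparison: the costs of the DTS procedure are evaluated, "comparing them to those incurred for the execution of the CT in the subjects positive to the DTS". It does not say whether this is a cost per examination or a total, from whose perspective it is counted, or at what prices.

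The kind of CT is fixed elsewhere. The synopsis (Overall study design) says: "The subjects with one or more nodules larger than 5 mm, not clearly benign, will undergo diagnostic contrast enhanced CT". Section 4 repeats that these subjects "will undergo diagnostic contrast enhanced CT".

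Section 10.1.2 names the comparator: "The results are compared to the data obtained from the NELSON study and the National Screen Screening Trial". The stated purpose is the effectiveness of screening on ten-year lung cancer mortality. The synopsis background identifies the NLST as a low-dose CT trial, and Section 1 speaks of "high-risk subjects enrolled in screening trials performed with low-dose Chest CT".

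On funding, Section 20 says that the hospital, "thanks to a donation of Fondazione CRC, will cover costs of DTS examination". The synopsis background adds that the DTS technology itself came from a donation by the same foundation.

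**The concern.** A cost-effectiveness comparison needs the cost and the effect of the same strategy. Here the effect on the CT side comes from screening with low-dose CT, which every screened person receives. The cost on the CT side comes from a different procedure, a contrast-enhanced diagnostic scan, done only in those whom DTS has already selected. That scan belongs to the DTS strategy as its work-up; it is not the alternative to DTS.

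If Section 10 is followed as written, the result does not answer whether DTS is good value against CT screening. That question matters to the study's case, because the synopsis background presents DTS as cheaper than CT and Section 1 lists high cost among the drawbacks of CT. The primary endpoint, the lung cancer detection rate, is not affected.

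**Working it through.** The plan states no price, cost ratio or cost-effectiveness ratio, so there is no figure of its own to reproduce. The check is what the stated rule yields under each reading that the text allows.

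**Inputs**
- Price of a low-dose CT: set to 1 as the unit.
- Price of a contrast-enhanced CT: k units. The documents give no prices. Assumed range 1.2 to 2.0 for the per-examination figure, and 1 to 3 for the aggregate figure so as to include no price difference.
- Share of screened subjects sent to CT: q. The synopsis background gives DTS abnormality rates in the SOS trial of 14.5% at baseline and 0.7% one year later. These are proxies: they are not referral rates under the 5 mm rule, and the five-year rate is unknown.
- Price of a DTS examination: d units, assumed, for illustration only.

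**Per-examination reading.** The contrast CT price stands in for the price of a screening CT. Error = k − 1:
- k = 1.2: +20%
- k = 1.5: +50%
- k = 2.0: +100%

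CT screening is overpriced whenever k > 1.

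**Aggregate reading.** CT costs are summed over DTS-positives and set against DTS costs in everyone. CT cost per screened subject = q × k, where CT screening of everyone would cost 1:
- q = 0.145: 0.145 × 1 = 0.145 up to 0.145 × 3 = 0.435, an error of −85.5% to −56.5%
- q = 0.007: 0.007 × 1 = 0.007 up to 0.007 × 3 = 0.021, an error of −99.3% to −97.9%

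CT is now underpriced. This would change only if k exceeded 1/q, that is 1/0.145 = 6.9 or 1/0.007 = 143.

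**Matched comparison.** DTS strategy = d + q × k; CT strategy = 1. The apparent saving from DTS per screened subject at q = 0.145 and k = 1.5 (so q × k = 0.2175) is:

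| Assumed d | Per examination, k − d | Aggregate, qk − d | Matched, 1 − (d + qk) |
|---|---|---|---|
| 0.3 | 1.20 | −0.08 | 0.48 |
| 0.8 | 0.70 | −0.58 | −0.02 |

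Neither reading of the rule recovers the matched figure, and the two err in opposite directions. At d = 0.3 the aggregate reading has the wrong sign; at d = 0.8 the per-examination reading does. Work-up after a positive low-dose CT is left out of this sketch; it would add to the CT side.

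**The case against.** A reader might infer that the rule prices CT screening too high and so makes DTS look cheaper than it is. The documents do not support that. It needs three premises: that contrast CT costs more than low-dose CT, that the comparison is per examination, and that this cost will stand as the price of CT screening. The first is plausible but nowhere stated, and the other two are not specified. Section 10.1.2 uses the external trials for effectiveness, not for unit costs. Read as costs incurred, the rule is at least as naturally an aggregate, and the bias then runs the other way.

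Three further inferences also go too far:
- That no low-dose CT cost will be observed at all. The table in Section 22.1.2 includes low-dose CT follow-up at three and six months, so some such scans could occur in DTS-positives. The synopsis timelines say that no follow-up is foreseen, which leaves this unclear.
- That donated DTS costs will be left out. Section 20 describes financing, and Section 10 says that DTS costs are evaluated. Omission is possible because no cost basis is stated, but it is not planned.
- That the sign of the result will generally reverse. With work-up charged to DTS but CT screening priced per examination as contrast CT, the sign is wrong only if d exceeds 1 − qk. At 14.5% this limit is 0.826 for k = 1.2 and 0.710 for k = 2.0; at 0.7% it is about 0.99. DTS would have to cost nearly as much as a low-dose CT or more in many of these cases, and the synopsis says that it costs less than CT.

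It is also true that NELSON is tied to low-dose CT only through the general description in Section 1, and that only the NLST is identified by name (taken here to be the national trial meant in 10.1.2). These objections remove the claim about direction. They do not remove the mismatch, which holds under either reading.

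**Conclusion.** The concern holds as a mismatch. Section 10 takes its CT cost from contrast-enhanced diagnostic CTs in DTS-positives, and Section 10.1.2 borrows effectiveness from low-dose CT screening. The comparison therefore does not estimate the cost-effectiveness of DTS against CT screening.

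The direction and size of the bias cannot be determined from the plan. CT screening is overpriced by k − 1 on one reading and underpriced by more than half on the other, at the proxy positive rates and for price ratios up to 3. All these sizes rest on assumed price ratios and on SOS abnormality rates used in place of the unknown five-year referral rate. The matter touches one secondary endpoint, and it should be corrected because the correction is cheap and works under either reading.

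**What to change.** In Section 10:
1. Cost the CT-screening strategy as the unit cost of a non-contrast low-dose CT (tariff or hospital cost), applied to every screened subject.
2. Charge the contrast-enhanced CTs in DTS-positives to the DTS pathway as work-up.
3. Value DTS and CT on the same full-cost basis, including donated equipment and examinations, and state the cost unit and perspective.
4. Say how work-up after a positive screening CT is treated, so that both strategies are charged alike.

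The cost is a few sentences and one extra tariff to look up, with no new data from subjects. The drawback for the sponsor is that the stated cost advantage of DTS may become smaller.

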10.1. Methods

10.1.1. Type of Economic Evaluation.

Since a predictable variance in effectiveness, a cost-effectiveness analysis is justified.

10.1.2. Choice of Comparator.

The results are compared to the data obtained from the NELSON study and the National Screen Screening Trial for the evaluation of the effectiveness of screening in the control of 10-year mortality due to lung cancer.

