Sample size	
The primary objective of this study is to calculate the detection rate on lung cancer at 5 years distance from the previous DTS. In the SOS study 1843 subjects were enrolled and lung cancer was found in 18 (0.8%) of them at baseline. 1703 subjects performed the first round DTS at one-year distance and lung cancer was found in 5 (0.3%) of them.
 
The number of patients needed to be confident that the disease will be detected if present at or above the specified prevalence of 0.3% with a confidence of 5% (i.e. assuming that the true prevalence is at least 0.3%, then a sample consisting only of subjects without lung cancer would occur 5% of the time or less given a sample with the calculated size) is 998. Allowing for a drop out of no more than 50%, a minimum number of 1496 subjects is required.

Timelines	
Expected accrual time: September 2017 / August 2018
 
Patients with positive TC will be subjected to diagnostic investigations to identify the pathology according to Fleischner Society. Length of Follow-up: no follow-up is foreseen for these patients

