Background and rationale	
Lung cancer is the leading cause of cancer-related death around the world. In 2008 there were nearly 1.6 million new cases worldwide, accounting for the 12.7% of all new cancer diagnoses[4]. Despite decreasing trends in smoking and resulting decrease in lung cancer mortality, the population at risk for lung cancer continues to be large[5]. In the past years several programs have been developed to screen for lung cancer using low-dose chest computed radiography (CT). However, only recently different studies demonstrated a clear reduction in mortality[5,6]. In particular, NLST low dose CT screening trial demonstrated a 6.7% reduction in the death rate compared to chest X-ray with a positive screening test rate for lung cancer detection of 24.2%, compared to 6.9% for conventional X-ray[7]. The use of CT as a screening test has nonetheless recently prevailed over the concern for the cost and the radiation burden[8]. Digital tomosynthesis (DTS) is a limited angle tomography that allows reconstruction of multiple image planes from a set of projection data acquired over a relatively small angle of X-ray tube movement[9]. Santa Croce and Carle Hospital has this technology from March 2010, thanks to a donation of Fondazione CRC. Although it does not have the spatial depth resolution of computed tomography, it provides high-resolution images in the sagittal planes at a lower dose and cost than CT[10]. Several studies have shown that DTS offers advantages over conventional chest X-ray and comparable of those of CT[11–13]. The Studio OSservazionale (SOS) was a clinical trial conducted within Santa Croce e Carle Hospital sponsored by Fondazione CRC analysing smokers and former smokers aged 45–80 with no cancer diagnosis. All the subjects in whom a suspicious nodule was detected by DTS underwent diagnostic CT. The SOS study demonstrated that baseline DTS detected pulmonary abnormalities in 14.5% and lung cancer in 1.0% of the subjects[14], comparable to results obtained in CT screening programs. A second DTS, within the same study, executed one year later reported pulmonary abnormalities in 0.7% and lung cancer in 0.3% of the subjects[15].

1. Background and introduction

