5.3. Cost-effectiveness

Related end-points are defined in the Chapter on "Economic evaluation" (chapter 10).

6. Statistical considerations

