6.3. End of study

End of study befalls when all of the next criteria have been satisfied:

1. One year after start-up
2. At least 80% of the subjects enrolled in SOS trial have been contacted
3. The database has been fully cleaned and frozen for the analysis

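### Section 10.1.2 rests effectiveness on 10-year lung cancer mortality, which the stated schedule does not observe and a single cohort cannot attribute to DTS; chapter 10 names no other effect unit

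*Combined protocol and SAP*

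**What the plan says.** Section 5.3 refers the economic end-points to chapter 10. That chapter contains four things:

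- A cost comparison. The cost of DTS is recorded, "comparing them to those incurred for the execution of the CT in the subjects positive to the DTS".
- A type of evaluation (10.1.1): "Since a predictable variance in effectiveness, a cost-effectiveness analysis is justified".
- A comparator (10.1.2): NELSON and a second national screening trial, "for the evaluation of the effectiveness of screening in the control of 10-year mortality due to lung cancer".
- A population (10.1.3): the one fixed by the study's eligibility criteria.

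On design, chapter 4 says that "about 1700 subjects, who have been enrolled in SOS Observational Study will undergo a DTS". No control group is described.

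On duration, the Synopsis plans accrual from September 2017 to August 2018. Section 6.3 ends the study when three criteria are all met: "One year after start-up", at least 80% of SOS subjects contacted, and the database frozen. After a sentence about patients with a positive CT, the Synopsis Timelines add that "no follow-up is foreseen for these patients". Section 5.1 defines overall survival from randomization, with a minimum of five years of follow-up.

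**The concern.** A cost-effectiveness analysis needs an effect unit, a time horizon and a comparison that can be interpreted. The only effectiveness outcome in chapter 10 is ten-year lung cancer mortality, and the rest of the protocol schedules nothing that would measure it. The chapter gives no model or extrapolation to bridge the gap, no cost-effectiveness ratio, and no method for the comparison with the external trials.

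If the comparison were made as written, short observation would yield few deaths. If time were counted from SOS baseline, survivor selection would remove more. Both would make DTS look favourable beside trials that follow people from their own entry, and neither would be an effect of DTS.

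**Working it through.** **The plan's own figure.** Section 6.1.1 gives 998 subjects. With a rate of 0.3% and a 5% chance of seeing no case, n = ln(0.05)/ln(1 − 0.003) = 997.08, rounded up to 998; check: 0.997^998 = 0.0499. The figure reproduces. It is the number needed to see at least one lung cancer, and gives no basis for a mortality comparison.

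**Observation time on the stated schedule.**

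- After the study DTS: entry runs from September 2017 to August 2018. With close-out near the one-year minimum, each subject has 0 to about 1 year, mean about 0.5 year if accrual is even. That is at most 1/10 of the horizon named.
- From SOS baseline: section 2.1 places this DTS 5 years after the baseline exam. Section 6.1.1 places it 5 years after the previous DTS, which is about 6 years after baseline if the previous DTS was the one-year round. Adding 0 to 1 year gives about 5 to 7 years.
- Outer limit: the Background says the hospital "has this technology from March 2010". March 2010 to the end of August 2018 is 8.5 years. This runs to the last planned entry, so it is not a ceiling on observation. A subject scanned in that first month would need another 10 − 8.5 = 1.5 years to reach ten.

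**If section 5.1 governed.** Five years after the study DTS is still half of ten. Counted from SOS baseline it is 5 + 5 = 10 years.

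**Who is followed on that second count.** Section 10.1.3 uses the eligible population. Eligibility requires standing for the acquisition with a breath-hold and no cancer in the previous ten years, and the Synopsis adds no confirmed lung cancer. Nobody in this set can have died, or had lung cancer confirmed, before the study DTS. About 5 of the 10 years therefore contribute no lung cancer deaths by construction, and mortality since SOS baseline is biased downwards.

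**Expected cancers.** The lower yield is the plan's 0.3%. The upper yield is an assumption that 0.3% per year accumulates over five years: 1 − 0.997^5 = 1.49%.

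| Examined | At 0.3% | At 1.49% |
|---|---|---|
| 998 (section 6.1.1) | 3.0 | 14.9 |
| 1700 (chapter 4) | 5.1 | 25.3 |

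**Expected lung cancer deaths after the study DTS.** The documents give no usable rate. Assuming 1 to 5 per 1000 person-years and a mean of 0.5 year:

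- 998 × 0.5 × (0.001 to 0.005) = 0.5 to 2.5 deaths
- 1700 × 0.5 × (0.001 to 0.005) = 0.9 to 4.3 deaths

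Over a full ten years the same rates would give about 10 to 50 and 17 to 85.

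**The case against.** Several readings that a reader might infer go further than the documents allow.

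- *The study closes after exactly one year.* All three criteria in section 6.3 must be met, so one year is a minimum. However, the other two concern contacting subjects and freezing data, and neither schedules follow-up.
- *Nobody is followed.* The no-follow-up sentence comes after one on CT-positive patients and is not plainly about the whole cohort. Section 5.1 asks for five years, and the checklist in 22.2.4 lists a follow-up form. What stands is that these statements conflict. The CT-positive group also contains the cancers found through DTS, whose deaths matter most here.
- *Ten years is impossible on any count.* It is reachable if section 5.1 governs and time runs from SOS baseline.
- *Participants' mortality is too low relative to any trial.* Being alive and undiagnosed at entry is normal for a screening cohort. Counted from the study DTS it is not in itself a bias, and participants are about five years older than at SOS entry, which pushes mortality up. The bias is clear only when time runs from SOS baseline, and section 10.1.2 does not say where time starts.
- *Those who decline are lost.* They are offered a phone interview that covers their status. This helps the general mortality endpoint, but chapter 10 does not bring it into the economic evaluation.
- *The study has no usable effectiveness measure.* It does: detection rate and the percentage sent to radical surgery are Synopsis endpoints. Chapter 10 simply does not use them.

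Finally, the ten-year phrase may only describe what the external trials evaluated. On that reading, chapter 10 names no effect unit at all, so the need for one remains.

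**Conclusion.** The point holds in bounded form. Chapter 10's only effectiveness outcome has a ten-year horizon, against about 0 to 1 year after the study DTS and roughly 5 to 7 years from SOS baseline on the stated schedule. The five-year clause in section 5.1 conflicts with the Timelines and section 6.3, and refers to a randomization that the design lacks. Applying it reaches ten years only on the count that builds in survivor selection. Under every reading there is no control arm, so no mortality difference could be attributed to DTS.

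The timing conclusion rests on the protocol's own dates. The counts of 3 to 25 cancers rest on the assumed yield of 0.3% to 1.5%, and the counts of deaths on a rate assumed from outside the documents.

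A reader might infer that the whole economic conclusion fails. The documents do not support that: the DTS and CT cost comparison stands apart from the mortality outcome, and no decision rule is given. Cost-effectiveness is a secondary endpoint and the primary endpoint is unaffected, but the change should be made before analysis.

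**What to change.** 1. Rewrite section 10.1.2 so that the effectiveness units are histologically proven lung cancers detected and the share of them sent to radical surgery, for example with cost per cancer detected as the ratio. Give an interval with it, since the count will be small.
2. Restrict the external comparison to a description of positive-screen and detection rates, stating the differences in screening interval and population. The documents do not show whether the external trials offer a round at a similar interval.
3. State that no mortality effectiveness claim will be made.
4. Reconcile the follow-up statements in the Synopsis Timelines and sections 5.1 and 6.3, and give overall survival a time origin that exists in this study.

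The effect units are already Synopsis endpoints, and chapter 5 already requires histological proof, so items 1 to 3 need no new data. The cost is wording in 10.1.2 and alignment of the mortality and survival text. The sponsor gives up a mortality comparison that the design cannot support.
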